#### 6.5. Method of blinding and breaking the study blind

Data pertaining to RTS,S/AS02D or Engerix-B will be collected in a double blinded (observer blinded) manner; data relating to TETRActHib will be collected in an open fashion. 'Double blinded (observer blinded)' means that the vaccine recipient and their parent(s)/guardian(s) as well as those responsible for the evaluation of safety,

immunogenicity and efficacy endpoints will all be unaware which treatment, RTS,S/AS02D or Engerix-B, was administered to a particular subject. The only study staff aware of the vaccine assignment for RTS,S/AS02D or Engerix-B will be those responsible for the preparation and administration of vaccines; these staff will play no other role in the study.

Code break envelopes, for each study enrolled subject and associating each treatment number with a specific vaccine, will be kept in a safe and locked place with no access for unauthorized personnel by the Local Safety Monitor in Mozambique as well as by Central Safety at GlaxoSmithKline Biologicals, Rixensart.

If deemed necessary for reasons such as safety, the Local Safety Monitor in Mozambique as well as GSK Biologicals Central Safety will unblind the specific enrolled subject without revealing the study blind to the investigators.

One interim analysis will be conducted during the study: an analysis of Safety and Immunogenicity post Clinic Visit 10. To maintain the blind the interim analysis will be performed by a statistician independent of the GSK Biologicals, MVI and CISM clinical teams.

A formal reporting and analysis plan (RAP) will be developed. Once the study is completed and the GSK Biologicals reference database locked, GlaxoSmithKline Biologicals will be responsible for initiating the execution of the statistical analysis plan in collaboration with CISM and MVI and breaking the blind.

GSK Biologicals' policy (incorporating ICH E2A guidance, EU Clinical Trial Directive and Federal Regulations) is to unblind any serious adverse event (SAE) report associated with the use of the investigational product, which is unexpected and attributable/suspected, prior to regulatory reporting. The Clinical Safety physician is responsible for unblinding the treatment assignment in accordance with specified time frames for expedited reporting of SAEs (Refer to Section 8.8).

#### 6.6. Replacement of unusable vaccine doses

Additional vaccine doses will be provided to replace those that are unusable (see Appendix G for details of supplies).

In addition to the vaccine doses provided for the planned number of enrolled subjects, 5% additional doses will be supplied. In case a vaccine dose is broken or unusable, the investigator should replace it with a replacement vaccine dose. If a vaccine dose needs replacement, the envelope with the corresponding treatment number will designate the replacement without unblinding the study using a coded letter system. Although the sponsor need not be notified immediately in these cases, documentation of the use of the replacement vaccine must be recorded by the investigator on the vaccine administration page of the CRF and on the vaccine accountability form.

#### 6.7. Packaging

See Appendix G.

#### 6.8. Vaccine accountability

See Appendix G.

#### 6.9. Concomitant medication/treatment

At each study visit/contact, the investigator should question the enrolled subject's parent(s)/guardian(s) about any medication(s) taken.

All antipyretic, analgesic, antibiotic and antimalarial drugs, administered at ANY time during the period starting with administration of each dose and ending 30 days after each dose are to be recorded with generic name of the medication (trade names are allowed for combination drugs, i.e., multi-component drugs), medical indication, total daily dose, route of administration, start and end dates of treatment.

All antimalarial drugs administered during the period starting at 31 days post Dose 3 of RTS,S/AS02D and ending with the last visit for ADI are to be recorded with generic name of the medication (trade names are allowed for combination drugs, i.e., multi-component drugs), medical indication, total daily dose, route of administration, start and end dates of treatment (Amended 12 April 2005).

Any treatments and/or medications which are listed as elimination criteria in Section 4.5, e.g., any immunoglobulins, other blood products and any immune modifying drugs administered within three months preceding the first dose or at any time during the study period are to be recorded with generic name of the medication (trade names are allowed for combination drugs only), medical indication, total daily dose, route of administration, start and end dates of treatment. Refer to Sections 4.4 and 4.5. *The time periods between which each type of concommitant medication/treatment should be recorded is summarized in Table 24.* 

### Table 24Summary of time periods between which different classes of
concommitant medication/treatment must be recorded

3 months prior to Dose 1 $\rightarrow$ Dose 1	All treatments listed as elimination criteria in Section 4.5*
Dose 1 $\rightarrow$ 30 Days post Dose 3	All antipyretic, analgesic, antibiotic, antimalarial and any
	treatments listed as elimination criteria in Section 4.5*
31 Days post Dose 3 $\rightarrow$ last visit for ADI	All antimalarial drugs and treatments listed as elimination
	criteria in Section 4.5*
Last visit for ADI $\rightarrow$ Final Study Visit	All treatments listed as elimination criteria in Section 4.5*

\* e.g. any immunoglobulins, other blood products and any immune modifying drugs (Amended 12 April 2005).

Any vaccine not foreseen in the study protocol administered in the period beginning 30 days preceding each dose and ending 30 days after each dose is to be recorded with trade name, route of administration and date(s) of administration. Refer to Sections 4.4 and 4.5.

Any concomitant medication administered prophylactically in anticipation of reaction to the vaccination must be recorded in the CRF with generic name of the medication (trade names are allowed for combination drugs only), total daily dose, route of administration, start and end dates of treatment and coded as 'Prophylactic'.

### 7. HEALTH ECONOMICS

Not applicable

#### 8. ADVERSE EVENTS AND SERIOUS ADVERSE EVENTS

The investigator is responsible for the detection and documentation of events meeting the criteria and definition of an adverse event (AE) or serious adverse event (SAE) as provided in this protocol. During the study, when there is a safety evaluation, the investigator or site staff will be responsible for detecting AEs and SAEs, as detailed in this section of the protocol.

Each enrolled subject's parent(s)/guardian(s) will be instructed to contact the investigative team at CISM immediately should the enrolled subject manifest any signs or symptoms they perceive as serious.

#### 8.1. Definition of an adverse event

An AE is any untoward medical occurrence in a clinical investigation subject, temporally associated with the use of a medicinal product, whether or not considered related to the medicinal product.

An AE can therefore be any unfavorable and unintended sign (including an abnormal laboratory finding), symptom, or disease (new or exacerbated) temporally associated with the use of a medicinal product.

Examples of an AE include:

- Exacerbation of a chronic or intermittent pre-existing condition including either an increase in frequency and/or intensity of the condition.
- New conditions detected or diagnosed after investigational product administration even though it may have been present prior to the start of the study.
- Signs, symptoms, or the clinical sequelae of a suspected overdose of either investigational product or a concurrent medication (overdose per se should not be reported as an AE/SAE).
- Signs, symptoms temporally associated with vaccine administration.

AEs may include pre- or post-treatment events that occur as a result of protocolmandated procedures (i.e., invasive procedures, modification of subject's previous therapeutic regimen). N.B. AEs to be recorded as endpoints (solicited events) are described in Section 8.4.1. All other AEs will be recorded as **UNSOLICITED AEs**.

Example of events to be recorded in the medical history section of the CRF:

Pre-existing conditions or signs and/or symptoms present in a subject prior to the start of the study (i.e. prior to the first study procedure) should be recorded in the medical history section of the subject's CRF.

#### 8.2. Definition of a serious adverse event

A serious adverse event (SAE) is any untoward medical occurrence that:

- a) results in death;
- b) is life-threatening;

NOTE: The term 'life-threatening' in the definition of 'serious' refers to an event in which the subject was at risk of death at the time of the event. It does not refer to an event, which hypothetically might have caused death, if it were more severe.

c) requires hospitalization or prolongation of existing hospitalization;

NOTE: In general, hospitalization signifies that the subject has been detained (usually involving at least an overnight stay) at the hospital or emergency ward for observation and/or treatment that would not have been appropriate in the physician's office or outpatient setting. Complications that occur during hospitalization are AEs. If a complication prolongs hospitalization or fulfills any other serious criteria, the event is serious. When in doubt as to whether 'hospitalization' occurred or was necessary, the AE should be considered serious.

Hospitalization for elective treatment of a pre-existing condition that did not worsen from baseline is not considered an AE.

d) results in disability/incapacity;

NOTE: The term disability means a substantial disruption of a person's ability to conduct normal life functions. This definition is not intended to include experiences of relatively minor medical significance such as uncomplicated headache, nausea, vomiting, diarrhea, influenza, and accidental trauma (e.g. sprained ankle) which may interfere or prevent everyday life functions but do not constitute a substantial disruption.

e) is a congenital anomaly/birth defect in the offspring of a study subject;

f) medical or scientific judgement should be exercised in deciding whether reporting is appropriate in other situations, such as important medical events that may not be immediately life-threatening or result in death or hospitalization but may jeopardize the subject or may require medical or surgical intervention to prevent one of the other outcomes listed in the above definition. These should also be considered serious.

Examples of such events are invasive or malignant cancers, intensive treatment in an emergency room or at home for allergic bronchospasm, blood dyscrasias or convulsions that do not result in hospitalization.

In this study all seizures occurring within a 30-day period of vaccination will be notified as SAEs. Complete data collection of seizures is sought to pilot an analysis proposed by the Brighton Collaboration [Bonhoeffer, 2004]. Key information pertaining to seizures will be documented in the CRF.

# 8.3. Clinical laboratory parameters and other abnormal assessments qualifying as adverse events and serious adverse events

Abnormal laboratory findings (e.g., clinical chemistry, hematology, urinalysis) or other abnormal assessments (e.g. blood film) that are judged by the investigator to be clinically significant will be recorded as AEs or SAEs if they meet the definition of an AE, as defined in Section 8.1 or SAE, as defined in Section 8.2. Clinically significant abnormal laboratory findings or other abnormal assessments that are detected during the study or are present at baseline and significantly worsen following the start of the study will be reported as AEs or SAEs. However, clinically significant abnormal laboratory findings or other abnormal assessments that are associated with the disease being studied, unless judged by the investigator as more severe than expected for the subject's condition, or that are present or detected at the start of the study and do not worsen, will not be reported as AEs or SAEs.

The investigator will exercise his or her medical and scientific judgement in deciding whether an abnormal laboratory finding or other abnormal assessment is clinically significant.

# 8.4. Time period, frequency, and method of detecting adverse events and serious adverse events

All AEs occurring within 30 days following administration of each dose of vaccine must be recorded on the Adverse Event form in the subject's CRF, irrespective of severity or whether or not they are considered vaccination-related.

The standard time period for collecting and recording SAEs will begin at first receipt of vaccine and will end at the study conclusion. See Section 8.7 for instructions for reporting and recording SAEs.

Additionally, in order to fulfill international reporting obligations, SAEs that are related to study participation (e.g. procedures, invasive tests, a change from existing therapy) or are related to a concurrent medication will be collected and recorded from the time the subject consents to participate in the study until she/he is discharged: if a child is screened and enrolled, then discharge will be the end of the study as per study protocol; if a child is screened but not enrolled, then discharge will be the point at which the decision is taken not to enroll the child.

The investigator will inquire about the occurrence of AEs/SAEs at every visit/contact during the study and throughout the follow-up phase as appropriate.

The mechanism by which SAEs will be identified in the study are detailed in Section 5.1.14. The investigator or study clinician will fully document any such events on the Serious Adverse Event pages appended to the individual Case Report Form including, where applicable, information from relevant hospital case records, autopsy reports and verbal autopsies.

All AEs either observed by the investigator, study clinician, field worker or reported by the subject's parent/guardian spontaneously or in response to a direct question will be evaluated by the investigator. AEs not previously documented in the study will be recorded in the Adverse Event form within the subject's CRF. The nature of each event, date and time (where appropriate) of onset, outcome, intensity and relationship to vaccination will be established. Details of any corrective treatment will be recorded on the appropriate page of the CRF. Refer to Section 6.9.

As a consistent method of determining the occurrence of unsolicited AEs, the subject or the subject's parent/guardian will be asked a non-leading question such as:

'Has your child acted differently or felt different in any way since receiving the vaccine or since the last visit '

N.B. The investigator should record only those AEs having occurred within the time frame defined above.

AEs already documented in the CRF, i.e. at a previous assessment, and designated as 'not recovered/not resolved' or 'recovering/resolving' should be reviewed at subsequent visits, as necessary. If these have resolved, the documentation in the CRF should be completed.

N.B. If an AE changes in frequency or intensity during the specified reporting period, a new record of the event will be entered.

When an AE/SAE occurs, it is the responsibility of the investigator to review all documentation (e.g., hospital progress notes, laboratory, verbal autopsies and diagnostics reports) relative to the event. The investigator will then record all relevant information regarding an AE/SAE on the CRF or SAE Report Form as applicable. It is not acceptable for the investigator to send photocopies of the subject's medical records to GSK Biologicals in lieu of the appropriate completed AE/SAE pages. However, there may be instances when copies of medical records and verbal autopsies for certain cases are requested by GSK Biologicals. In this instance, all subject identifiers will be blinded on the copies of the medical records prior to submission to GSK Biologicals.

The investigator will attempt to establish a diagnosis of the event based on signs, symptoms, and/or other clinical information. In such cases, the diagnosis should be documented as the AE/SAE and not the individual signs/symptoms.

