- After vaccination, trained field workers will visit the children to detect adverse events (AEs) occurring after vaccination for one week (days 1, 2, 3, 4, 5 and day 6 after each vaccination). Data will be collected after all doses of RTS,S/AS02D or Engerix-B and all doses of TETRActHib. Diary cards and thermometers will be provided for the field workers to record axillary temperature and any local (at the injection site) or general adverse events.
- There will be a 14 day follow-up period after each Dose of TETRActHib and Dose 1 and Dose 2 of RTS,S/AS02D or Engerix-B, and a one month (30 day) follow-up period after Dose 3 of RTS,S/AS02D or Engerix-B for reporting unsolicited symptoms
- Infants will be followed for 14 months after administration of the first dose of TETRActHib.
- Recording of serious adverse events will be throughout the study period. They will be captured through the morbidity surveillance system at Ilha Jossina Health Center, *Taninga Health Center* and Manhiça District Hospital. In addition all enrolled children will be visited at home monthly by field workers until study conclusion to ensure complete identification of all SAEs (*Amended 29 June 2005*).Bloods for safety monitoring of hematology, renal and hepatic function will be measured at 1 week post Dose 1, one month post Dose 3, 3½ months post Dose 3 and 12 months post Dose 3 of RTS,S/AS02D or Engerix-B.
- Non inferiority of hepatitis B response will be determined one month post Dose 3 of RTS,S/AS02D or Engerix-B.
- Anti-CS antibody titers will be determined at baseline, one month post Dose 3, 3/2 months post Dose 3 and 12 months post Dose 3 of RTS,S/AS02D or Engerix-B.
- Anti-HBs antibody titers will be determined at baseline, one month post Dose 3 and 12 months post Dose 3 of RTS,S/AS02D or Engerix-B.
- Two weeks prior to Dose 3 of TETRActHib *RTS*,*S*/*AS02D*, children will be treated with sulfadoxine-pyrimethamine and Amodiaquine for presumptive clearance of parasitemia (*Amended 12 April 2005*).
- All children will have a blood slide prepared and read to check for asexual *P*. *falciparum* parasitemia on the day of receiving Dose 3 of RTS,S/AS02D. Any children who test positive will be excluded from ADI.

- The total period of surveillance for ADI is 12 weeks. Seven visits will contribute to the ADI, made up of four field-worker visits and three clinic visits.

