The process for each vaccination is as follows. The identity of the child will be confirmed using the study identification card. The subject number on this card will be cross-checked with that on the subject's clinic form, ensuring that the subject number on the clinic form matches that of the study identification card. On the day of the first vaccination the inclusion/exclusion criteria and consent form will be checked prior to vaccination. On the days of the subsequent vaccinations, elimination criteria and contraindications to vaccination will be checked prior to vaccination. A vaccine clinic form will be initiated, which will give the child's identifiers, subject number and treatment number assigned after the administration of the vaccine.

For each vaccination during the course of the study, the Vaccinator will prepare and administer the vaccine for a specific subject. Since the vaccines used in this study are of distinct appearance, the Vaccinators are not blinded and perform no other function in the study (refer to Section 6.5). The Vaccinator will select the sealed box labeled with the subject's treatment number, containing the vials numbered with the treatment number, remove the vaccine vials and fill a syringe according to this study protocol (refer to Section 6.2). The Vaccinator will then place a numbered opaque label with the subject's treatment number on the syringe. The purpose of masking the syringe is to blind the parent(s) or guardians(s) of the subject. After administering the vaccination to the subject the Vaccinator will enter the treatment number administered to the subject on the clinic form.

Subjects who cannot be vaccinated on the originally scheduled date (due to an acute illness on the judgment of the PI or designate, local lesion at the injection site or scheduling conflicts) will be vaccinated within 7 days and undergo all study procedures

for the visit on the same day as vaccination. In the particular case of any child found to be febrile (axillary temperature  $\geq 37.5^{\circ}$ C), a blood slide will be taken to investigate for malaria. Children will be treated as appropriate for their condition and will be followed up until resolution of any symptoms and be vaccinated if their clinical symptoms resolve within 7 days.

Those who cannot be re-vaccinated within 7 days of their scheduled date will continue all study procedures apart from receiving further study vaccinations.

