#### 5.3. Outline of study procedures

#### SCREEN DOUBLE-BLIND PHASE SINGLE-BLIND PHASE VACCINATION ADI Study Months 0 2 Z 4-5 6 7-13 14 74 -14 to 0 0 14 21 30 44 60 90 104 180 Study days Age (approx. weeks) 6 to 8 10 11 12 14 18 20 22 30 70 8 16 32 Clinic Visit 6 7 8 9 10 12 1 2 3 4 5 11 Field Worker Visit Code # 21-26 27-31 32-37 38-43 44-49 50-55 56-59 60-66 STUDY PROCEDURES Informed consent • Check of inclusion/ \* ٠ exclusion criteria Medical history \* • Physical examination \* • \* \* \* \* \* \* \* \* \* Measure body weight • \* \* • \* • Check contraindications • • • • • • to vaccination Temperature • • • • • • • • • ٠ ٠ ٠ • Randomization • Vaccination—RTS,S/AS02D or • • • Engerix-B Vaccination—TETRActHib . ٠ . Check of elimination criteria • • • • • • • • • Recording of medication ٠ • • • • • ٠ • • • ٠ ٠ • • • • SAFETY DATA COLLECTION Post-vaccination recording of solicited symptoms by • • • • • • investigator (Day 0) Solicited symptoms by • investigator (Day 6) Solicited symptoms by field • • ٠ ٠ ٠ • workers Recording of unsolicited AEs up to 1 month (min. • • . . . • 14 days) post-vaccination by investigator Morbidity surveillance/ • b • • • • • • • • • • • • • • • • • • • recording of SAEs ACTIVE DETECTION OF INFECTION Administer drug for clearance • History of fever (for ADI) ٠ • ٠ ٠ Temperature (for ADI) . • • . LABORATORY ANALYSES Blood sampling • ٠ ٠ ٠ • ٠ ٠ ٠ Complete blood counta • • ٠ • • Creatinine, ALT, bilirubin • • ٠ ٠ • Antibodies to HBs • ٠ ٠ Antibodies to CS • ٠ ٠ ٠ Antibodies to Pertussis • . Antibodies to Diphtheria . Antibodies to PRP ٠ Antibodies to Tetanus ٠ Smear for parasite density ° ٠ ٠ ٠ ٠ ٠ Parasite genotyping • ٠ ٠ ٠ ٠ Cell-Mediated Immunity • ٠ ٠ Determinants of vaccine ٠ response INTERIM ANALYSIS SAFETY • & immunogenicity FINAL ANALYSIS • STUDY CONCLUSION •

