# 8.6. Follow-up of adverse events and serious adverse events and assessment of outcome

After the initial AE/SAE report, the investigator is required to proactively follow each subject and provide further information to GSK Biologicals on the subject's condition.

All AEs and SAEs documented at a previous visit/contact and designated as not recovered/not resolved or recovering/resolving will be reviewed at subsequent visits/contacts.

Investigators will follow-up subjects:

- with SAEs or subjects withdrawn from the study as a result of an AE, until the event has resolved, subsided, stabilized, disappeared, the event is otherwise explained, or the subject is lost to follow-up;
- or, in the case of other non-serious AEs, until they complete the study or they are lost to follow-up.

Clinically significant laboratory abnormalities will be followed up until they have returned to normal, or a satisfactory explanation has been provided. Additional

information (including but not limited to laboratory results) relative to the subsequent course of such an abnormality noted for any subject must be made available to the Study Monitor.

GSK Biologicals may request that the investigator perform or arrange for the conduct of supplemental measurements and/or evaluations to elucidate as fully as possible the nature and/or causality of the AE or SAE. The investigator is obliged to assist. If a subject dies during participation in the study or during a recognized follow-up period, GSK Biologicals will be provided with a copy of any available post-mortem findings, including histopathology and verbal autopsies.

New or updated information will be recorded on the originally completed SAE Report Form, with all changes signed and dated by the investigator. The updated SAE report form should be resent to GSK Biologicals within 24 hours of receipt of the follow-up information as outlined in Section 8.7.1.

Outcome of any non-serious AE occurring within 30 days post-vaccination (i.e. unsolicited AE) or any SAE reported during the entire study will be assessed as:

- Recovered/resolved
- Not recovered/not resolved
- Recovering/resolving
- Recovered with sequelae/resolved with sequelae
- Fatal (SAEs only).

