#### **10.2.** Secondary endpoints

#### 10.2.1. Secondary endpoints for Safety

• Occurrence of unsolicited AEs after Dose 1, 2 and 3 of TETRActHib over a 14 day follow-up period (day of vaccination and 13 subsequent days)

- Occurrence of unsolicited AEs after Dose 1 and 2 of RTS,S/AS02D or Engerix-B over a 14 day follow-up period (day of vaccination and 13 subsequent days)
- Occurrence of unsolicited AEs after Dose 3 of RTS,S/AS02D or Engerix-B over a 30 day follow-up period (day of vaccination and 29 subsequent days)
- Occurrence of solicited general and local reactions over a 7 day follow-up period (day of vaccination and 6 subsequent days) after TETRActHib
- Occurrence of solicited general and local reactions over a 7 day follow-up period (day of vaccination and 6 subsequent days) after RTS,S/AS02D or Engerix-B.

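### Unsolicited AEs are to be recorded for 30 days after every dose but are tabulated only for Days 0 to 13 after five of the six doses, so non-serious events from Day 14 to the next dose enter no unsolicited-AE table

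*Protocol*

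**What the plan says.** The protocol describes the unsolicited-AE window in three ways.

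- **30 days after each dose.** Section 8.4: "All AEs occurring within 30 days following administration of each dose of vaccine must be recorded". It then limits recording to that period: "The investigator should record only those AEs having occurred within the time frame defined above". Section 8.6 uses the same period and ties it to the term itself: "Outcome of any non-serious AE occurring within 30 days post-vaccination (i.e. unsolicited AE".
- **Up to a month, at least 14 days.** Table 20 in Section 5.3: "Recording of unsolicited AEs up to 1 month", with a minimum of 14 days in brackets.
- **14 days after five doses, 30 days after the sixth.** Section 3: "There will be a 14 day follow-up period after each Dose of TETRActHib and Dose 1 and Dose 2 of RTS,S/AS02D or Engerix-B", with 30 days after Dose 3 of the blinded vaccine. Section 10.2.1 makes this the endpoint. For the EPI vaccine it reads "after Dose 1, 2 and 3 of TETRActHib over a 14 day follow-up period". For the blinded vaccine the wording is "Occurrence of unsolicited AEs after Dose 1 and 2 of RTS,S/AS02D or Engerix-B over a 14 day follow-up period (day of vaccination and 13", which means Days 0 to 13; Dose 3 has a separate 30-day endpoint. Section 10.8.2 tabulates on the same windows.

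The visit procedures in Section 5.4 ask at each vaccination visit after the first for unsolicited AEs since the previous vaccination, which can reach beyond Day 13. Section 10.8 describes the 14- or 30-day unsolicited-symptom analysis at Clinic Visit 10 as final.

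**The concern.** Site staff have two collection rules. Under Section 8.4, an event starting on Day 15 after a first RTS,S/AS02D dose goes on the AE form. Under Section 3, it lies outside the reporting period. If it is recorded, Sections 10.2.1 and 10.8.2 still leave it out unless the next dose has already opened a new window.

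The gap is also not independent of health. Section 5.1.11 provides for deferral: "Subjects who cannot be vaccinated on the originally scheduled date (due to an acute illness on the judgment of the PI or designate", or for a local lesion or a scheduling conflict, with vaccination then to follow within 7 days. Deferral lengthens the interval, and the 14-day window does not lengthen with it. A fever that starts on the day a dose is due, and causes that dose to be put off, falls after the old window has closed and before the new one opens. By the Glossary, a solicited symptom with onset outside the solicited period is an unsolicited AE, so such a fever belongs in these tables.

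At stake is the completeness of the unsolicited-AE tables in the first trial of this formulation in infants, where safety is the primary objective.

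**Working it through.** The plan gives no figure for this, so the check is a count of days.

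**Inputs**
- Scheduled dose days (Section 5.4): 0, 14, 30, 44, 60, 74. TETRActHib is given on Days 0, 30 and 60, and the blinded vaccine on Days 14, 44 and 74.
- Recording window (Section 8.4): 30 days after each dose, read as Day 0 to Day 29 to match the endpoint definition. Reading it as Day 0 to Day 30 does not change the gaps between doses.
- Endpoint windows (Section 10.2.1): 14, 14, 14, 14, 14 and 30 days.
- Permitted dose-to-dose interval (Table 21): 12 to 21 days, for all five intervals.
- Deferral (Section 5.1.11): up to 7 days; after that no further study vaccine is given.

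**Formula.** For consecutive doses *g* days apart (up to 30), uncovered days = max(0, *g* − 14). Days falling in two windows = max(0, 14 − *g*).

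**Nominal schedule.** The intervals are 14, 16, 14, 16 and 14 days, so the gaps are 0, 2, 0, 2 and 0. Recorded days: 74 + 30 = 104. Endpoint days: 5 × 14 + 30 = 100. The 4 uncovered days (3.8%) are study Days 28, 29, 58 and 59. All four follow Doses 1 and 2 of the blinded vaccine, 2 of 16 days (12.5%) after each.

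**Range allowed by Table 21**

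| Case | Uncovered days |
|---|---|
| All intervals 12 days | 0 (2 days per interval lie in two windows) |
| One 14-day interval deferred to 21 days, the rest nominal | 7 + 2 + 2 = 11 |
| All five intervals 21 days | 5 × 7 = 35 of 105 + 30 = 135 (26%) |

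A 16-day interval deferred by 7 days becomes 23 days, with a gap of 9. That is outside Table 21, although Section 5.1.11 would permit it.

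**Course stopped early.** With no later dose there is no later window, so Days 14 to 29 after the last dose (16 days) are recorded but not counted. Adding the gaps before that point gives 16, 16, 18, 18 and 20 uncovered days for a course stopped after 1, 2, 3, 4 or 5 doses.

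**Which deferring illnesses are missed.** An illness that began by Day 13 is counted. In the three 14-day intervals, an illness already present at the visit is missed only if it started on the visit day (Day 14) and the dose was deferred. In the two 16-day intervals, it is missed if it started on Day 14 or 15, or on Day 16 with the dose deferred. Any further onset during the deferral itself is also uncovered.

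**The case against.** A reader might infer that illnesses arising late in an interval, including those that postpone a dose, are counted nowhere. The protocol does not support that. Dose 3 of RTS,S/AS02D or Engerix-B has a 30-day endpoint. On schedule, most of Days 14 to 29 after a dose lies inside the next dose's window. SAEs are collected to study conclusion (Section 8.4) and form the primary endpoint. Seizures within 30 days of vaccination are notified as SAEs (Section 8.2). Withdrawals due to AEs are described in detail (Sections 10.8.2 and 10.9.1.2). The DSMB reports in Section 5.1.5 tabulate unsolicited AEs by dose with no 14-day limit stated, though only at three data cuts. Most deferring illnesses may have begun by Day 13, and the protocol gives no rate for the others.

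It can also be said that collecting more than is tabulated is not an error, that Table 20 hints at that structure, and that a fixed 14-day window is reasonable for vaccines given about two weeks apart. The windows are the same in both arms, no between-group test is specified for unsolicited AEs, and double counting at short intervals does not affect an overall proportion of children with at least one event.

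All of this limits the size of the problem, and it argues for keeping the fixed window as the endpoint. It does not remove the conflict. Section 3 gives its 14 days as a reporting period, not just a tabulation rule, and Section 8.6 attaches 30 days to the term. The protocol itself fixes both windows, so this is not a detail left open for the analysis plan.

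**Conclusion.** The point holds in a limited form. The protocol sets a 30-day recording rule and a 14-day reporting and counting rule for the same five doses. Non-serious AEs that start on Day 14 or later and before the next dose, and do not lead to withdrawal, fall in no unsolicited-AE endpoint and no Section 10.8.2 table. They may go unrecorded where sites follow Section 3.

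On the nominal dates the loss is small: 4 of 104 days. It reaches 7 days in any interval stretched to 21 days, and 16 days after the last dose when a course stops early. The 35-of-135 figure needs every interval of one child at its maximum and should be read as a bound, not as typical.

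These counts assume that windows run from the day of vaccination and that Table 21 is respected. How many events are affected cannot be estimated from the protocol. No power or test result depends on it; the effect is on the completeness and consistency of a descriptive secondary safety endpoint. It is worth correcting because deferral for illness is one of the things that opens the gap.

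**What to change.** 1. State one recording window, 30 days after each dose as in Section 8.4, and bring Sections 3, 5.3 (Table 20), 8.4, 8.6, 10.2.1 and 10.8.2 (and the synopsis) into line with it. Say explicitly that recording is wider than the endpoint window.
2. Keep the fixed Day 0 to 13 tabulation, and 30 days after Dose 3 of RTS,S/AS02D or Engerix-B, as the endpoint.
3. Add to Section 10.8.2 one table by group of all recorded unsolicited AEs from the first dose to 30 days after the last dose received. Count each event once and attribute it to the most recent dose. Events from Day 14 to the next dose, and those after a course stopped early, are then reported.

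Replacing the endpoint window with one that runs to the next actual dose is not advised: children deferred for illness would be observed longer, so window length would depend on the outcome. The added table carries a mild form of the same drawback, since observation time in it varies slightly with deferral, and a footnote should say so. The cost is wording and one table. No extra data are needed where sites follow Section 8.4; where they have worked to Section 3, they need to be told which rule applies.
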